All participants will be interviewed in person, upon enrollment, prior to randomization, by a trained study team member. At the enrollment visit, baseline data will be collected on demographics, bio-psychosocial status, as well as COPD knowledge, self-management skills, patient activation, and health literacy levels. Participants will then be interviewed via phone by a research team member, who is blinded to their study group assignment at 3-, 6-, and 9-months post enrollment. Similarly, we will collect data from caregiver participants who will be surveyed upon enrollment, and at 3-, 6-, and 9-months follow up post enrollment. Due to the study end date, it will not be possible to collect 9-month follow-up data for participants who enrolled later in the study.

Additionally, information will be collected post enrollment on whether the patient has visited the ED or been re-hospitalized via Chesapeake Regional Information System for our Patients (CRISP). CRISP will be used determine whether the visit was COPD-related using a set of pre-determined discharge diagnoses.

Study Outcomes and Hypotheses

The study groups will be compared for the following outcomes:

Primary Outcome for Patient Participants:

1. Change in health-related quality of life (HRQOL) as measured by the St. George Respiratory Questionnaire (SGRQ) total score, from baseline to 6 months post-enrollment.

Hypothesis: Patients in the HCP PLUS Peer Support group will have a larger improvement in HRQOL (larger negative change in SGRQ score) at 6 months post discharge compared to baseline, than patients in the *HCP only* group.

Secondary Outcomes and Intermediate Measures for Patient Participants:

Secondary Outcomes:

1. Change in HRQOL based on SGRQ total score at 9 months post enrollment.

Hypothesis: Patients in the HCP PLUS Peer Support group will have larger improvement in HRQOL (larger negative change in SGRQ score) compared to baseline, than patients in the *HCP only* group.

2. Total number of COPD-related hospitalizations and ED visits at 3, 6, and 9 months post-enrollment.

Hypothesis: Patients receiving the HCP PLUS Peer Support will have a lower rate of COPD-related hospitalizations and ED visits than patients in the *HCP only* group.

3. Total combined number of *all cause* hospitalizations and ED visits at 3, 6, and 9 months post-enrollment.

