was calculated and was used to replace the value of the missing item responses before calculation of the scale/domain score. This approach weights the scale/domain score towards the respondent's mean response and is balanced by requiring a large majority of item responses to be available. If more than 25% of the item responses were missing, the scale/domain score was considered missing.

Statistical Analysis (PCORI Standard IR-1, RC-4)

Statistical summaries and distributions of patient characteristics will be reviewed by study site (JHBMC and HCGH) and by recruitment setting (inpatient and outpatient). Statistical summaries and distributions of patient and clinical characteristics will also be reviewed across study groups. Randomization of the patients to the study groups expects that on average the groups were balanced on characteristics that might affect the study results, such as socio-demographic and health status. Thus, no statistical tests to compare the groups on patient characteristics will be performed.¹¹

Exploratory analyses will be performed cross-sectionally at baseline, 3, 6, and 9 months post-discharge for each of the outcomes across the two study groups. This will provide an assessment of the outcomes' distributions, missingness patterns and the need for additional data review and quality assurance.

The main analysis approach for assessing the change in the primary outcome measure from baseline, as well as changes in secondary outcome measures from baseline, will consist of performing analyses of the treatment effect between the two study groups under intention to treat (ITT) adjusted for baseline measure, site, and recruitment setting.

Repeated outcomes in this study will be evaluated using generalized linear mixed random-effects (RE) models. The generalized linear mixed RE model reflects the study's interest in comparisons of change at the individual level, where the changes may be subject-specific and reflective of potentially unmeasured variables. This model also fits well with the approaches related to

missing data and heterogeneity of treatment effects discussed below. In particular, this approach will help us handle the missing 9-month data for participants who enrolled later in the study.

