The primary repeated outcome (SGRQ) will be evaluated using a linear mixed RE model. Within this model, the primary hypothesis about change in HRQOL from baseline to 6 months, will be evaluated by a hypothesis test of the interaction term between study group and the 6-month time variable.

For secondary outcomes, we will fit appropriate generalized linear mixed RE models based on the type of outcome variable. Continuous measures, such as for HERTH Hope Index or PROMIS support domain scores, will be assessed using linear mixed RE models. Binary outcomes, such as Morisky adherence to medication, will be assessed using logistic mixed RE models. Outcomes that are cumulative counts, such as number of hospitalizations and ED visits, will be assessed using Poisson or negative binomial mixed RE models, as appropriate. Differences in change in outcome from baseline to 3, 6, and 9-months between the study groups will be assessed by including interaction terms between the time variables and study group. We will assess significance by first testing the overall interaction between time and group. If the overall interaction is significant for an outcome measure, we will then estimate and test individual time differences accounting for multiple testing using a Bonferroni correction. Initially models will be adjusted only for baseline measure, site, and recruitment setting. We will also consider adjusting for patient characteristics such as age, gender, presence of caregiver, home oxygen use, and prior hospitalization.

Unadjusted survival analyses using Kaplan-Meier and log rank tests will be performed for *time to death or first COPD-related hospitalization or ED visit*. Statistical significance will be considered for $p < 0.05$.

Complier-Average Causal Effect (CACE) using Instrumental Variable Estimation

CACE: Primary Outcome

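### Hospital and ED visit counts must first pass a time-by-group interaction test, which under one unexcluded reading of the SAP cannot see a constant rate reduction

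*Combined protocol and SAP*

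**What the plan says.** The SAP's Statistical Analysis section assigns the models by outcome type: "Outcomes that are cumulative counts, such as number of hospitalizations and ED visits, will be assessed using Poisson or negative binomial mixed RE models". It then gives one rule for secondary outcomes. The first step is "We will assess significance by first testing the overall interaction between time and group". The second is conditional on it: "If the overall interaction is significant for an outcome measure, we will then estimate and test individual time differences", with a Bonferroni correction. No group main effect or rate ratio is named for the counts.

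The outcome is defined in the SAP's Study Outcomes and Hypotheses, item 2: "Total number of COPD-related hospitalizations and ED visits at 3, 6, and 9 months post-enrollment". The hypothesis is that the peer-support arm "will have a lower rate of COPD-related hospitalizations and ED visits". Item 4 hypothesises a lower total for all-cause visits. Protocol section 4 (Study Measures and Outcomes, measure 2) counts visits from enrolment.

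Two analyses of acute-care use sit outside the two-step rule. One is an unadjusted log-rank test of "time to death or first COPD-related hospitalization or ED visit". The other is the complier-average causal effect (CACE) analysis of acute-care utilisation.

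**The concern.** A time-by-group interaction asks whether the difference between arms changes over time. The visit hypotheses ask whether there is a difference at all. For scale scores with a baseline row the two questions coincide, because randomised arms start level and any later difference appears as an interaction. A count that starts at enrolment is zero there by construction, so it offers no usable baseline value on a log scale.

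Acute-care use is part of the research question in protocol section 2, and the SAP makes ITT the main approach. If the first step cannot respond to the hypothesised effect, the ITT analysis of visits would usually end there, without an effect estimate at any single time.

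**Working it through.** **Inputs from the documents.** 290 enrolled and randomised 1:1, so 290 / 2 = 145 per arm (SAP, Study Design). Totals at 3, 6 and 9 months. Alpha 0.05, taken as two-sided. The documents give no visit rate, dispersion, rate ratio or power for visits, so there is no planned figure to reproduce. The 145 per arm was sized for the SGRQ change score, with a standard deviation that is not stated.

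**Assumptions.** Log link (usual for these models, but not named in the SAP); 0.6 to 1.5 control visits per 9 months; gamma variation between patients with variance 1; rate ratios 0.7 and 0.5.

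**Step 1, algebra.** With monthly control rate λ and constant ratio RR, expected totals at month t are λt and λ·RR·t. The log ratio is ln(λ·RR·t) − ln(λt) = ln RR at every t.

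- RR 0.7: −0.357 at 3, 6 and 9 months. Contrasts with month 3: 0 and 0.
- RR 0.5: −0.693 at 3, 6 and 9 months. Contrasts with month 3: 0 and 0.

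This does not depend on the assumed rates or dispersion. Separate three-month interval counts as rows give the same zeros.

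**Step 2, what the result depends on.** Three conditions are needed together: these rows, a log link, and a group main effect with two interaction terms. If instead each visit has its own group term and there is no group main effect, the overall test has 3 df and contains the level difference. A pre-enrolment row also brings that difference into the interaction.

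**Step 3, simulated rejection rates** (145 per arm; ranges span the assumed control rates).

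| Test | RR 0.7 | RR 0.5 | Build-up, interval ratios 1 / 0.7 / 0.5 |
|---|---|---|---|
| Interaction, 2 df, robust errors | 4.9-5.9% | 4.9-5.9% | 33-69% |
| Interaction, Poisson random intercept | 0-0.07% | 0-0.07% | 2-12% |
| Joint group effects at 3, 6, 9 months, 3 df, robust | 27-47% | 78-96% | 48-82% |
| Interaction with a matching 12-month pre-enrolment row, robust | 26-58% | 75-99% | not run |
| Direct negative binomial, 0-6 months | 34-52% | 76-96% | about 11-15% |
| Direct negative binomial, 0-9 months | 41-60% | 88-98% | 34-51% |

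With no effect, the robust 2-df interaction test rejects 4.9-5.7%, so a halving of visits is practically indistinguishable from no effect. A negative binomial random-intercept model (control mean 1.0) gave no rejections in 308 fits at RR 0.7 or 0.5. The constant-ratio figures for the direct tests allow for 6% deaths and 25% of patients without the full nine months. Wider assumptions (0.75 to 3 visits per 9 months, variance 1 to 2) leave the 2-df result at 4.7-6.4% with robust errors and at most 0.3% with model-based errors.

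**Step 4, the analyses outside the rule.** At RR 0.7 and 0.5 the log-rank test rejects 28-34% and 70-85%. CACE on the 0-6 month count, by two-stage least squares with 60-80% adherence and an effect in adherers only, rejects 32-53% and 77-96%. CACE is significant while the robust interaction test is not in 30-52% of trials at 0.7 and 73-91% at 0.5.

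**The case against.** The strongest reply is that the SAP may not mean the failing model. The sentence before the rule speaks of differences in change since baseline at each of three times. Three differences need either a baseline row or one group term per visit, and the 2-df form has neither. The SAP also plans summaries of each outcome at baseline, and protocol section 4 says utilisation history will be collected. This stands in part: the stated rows alone do not make the interaction zero, and a reader who infers that they do goes further than the documents allow.

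Neither alternative is specified for counts. The pre-enrolment item listed in the section 7.b table is self-reported prior-year hospitalisations, which omits ED visits, whereas later visits come from CRISP records. The ticks for the visit row could not be aligned with columns in the text available, so a baseline entry cannot be ruled out. Prior hospitalisation appears only in a list of optional covariates: "age, gender, presence of caregiver, home oxygen use, and prior hospitalization". Even a hospitalisation-only reference row (assumed to be half of all visits) would give the interaction test 21-44% power at 0.7 and 62-96% at 0.5, so the choice matters and should be written down.

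A second reply is that a gradual effect is plausible: the peer events span six months and the respiratory care practitioner's session may come up to two months after enrolment. With a strong build-up, the robust interaction test outperforms a direct 0-6 month test. That also stands, and it shapes the fix.

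Two stronger inferences fail. One is that the trial could not detect a constant reduction: the log-rank and CACE analyses could, although they address first event or death, and the effect in adherers. The other is that a significant CACE beside a non-significant interaction would be two opposite conclusions. They test different things, so the pair would be confusing, not strictly contradictory.

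**Conclusion.** The concern holds conditionally. With the 3-, 6- and 9-month totals as rows, a log link and a group main effect plus interactions, the stated first step rejects at about the alpha level with robust errors, and well below it with model-based errors, under any constant rate reduction. On a strict reading, no ITT rate ratio at individual times would then be produced. The zero interaction is exact under those conditions; every power figure rests on assumed rates, dispersion and effect sizes.

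Whether the trial would run that model is not settled by the text. What is settled is that the SAP applies a change-over-time test to an outcome whose hypothesis is a level difference, and names no ITT group test or rate ratio for it. This is worth fixing, with medium confidence. Only secondary outcomes are affected.

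**What to change.** Exempt visit counts from the interaction step and do one of the following:

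- Test the group coefficient in a negative binomial model for the 0-6 month count, with log person-time as offset and site and recruitment setting as covariates. Use 0-3 and 0-9 months as supporting windows.
- Alternatively, define the overall test as the joint test of the group effects at 3, 6 and 9 months with no separate group main effect. Use patient-level robust errors, because the totals overlap.

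Either way, report the ITT rate ratio with its 95% CI whatever the p-value. State which pre-enrolment count, if any, is the baseline measure for visits (events, window and source). Keep CACE and log-rank as supporting analyses.

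The cost is SAP wording and a few lines of code, with no new data. The drawback of the single 0-6 month test is low power for a strongly delayed effect (about 11-15% under the assumed rates). The 0-9 month window (34-51%) or the joint test (48-82%) reduces that loss. The joint test gives up some power when the reduction is constant.

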Given the nature of the HCP PLUS Peer Support group, it is not possible to guarantee full adherence from all of the patients. As a result, traditional ITT statistical methods might be biased due to the effects from non-adherent participants. To correct for this bias, we would implement an instrumental variable approach to estimate the effect of the intervention on the change in the HRQOL as measured by the SGRQ total score from baseline to 6-months post-enrollment.¹² One of the requirements for this analysis is to divide the group of patients assigned to the HCP PLUS Peer Support group into adherent and non-adherent participants. For our main analysis, we define as *adherent participants* all those patients who experienced at least 4 or more encounters with their peer mentor either by attending to a get-together, participated in a BREATHE call, or by having a phone conversation with their peer-pal. Phone conversations with peer-pals include both check-in conversations as well as conversations about the COPD related issues discussed at the get-togethers. For this analysis, we will instrument patient adherence with the patient's randomized assignment to either the control or the treatment group. Additionally, we will conduct sensitivity analyses by defining adherent participants to be (1) those participants with at least 2 encounters with their peers (get-togethers, BREATHE calls, or phone conversations) and (2) those participants who experienced at least 4 or more encounters with their peers either by attending to a get-together, participated in a BREATHE call, or by having a phone conversation with their BREATHE pal containing discussion of COPD-related issues (determination based on BREATHE pal notes.)

CACE: Secondary Outcomes

In order to analyze the effect of the Peer Support intervention on secondary outcomes such as the level of acute health care utilization (hospitalizations and ED visits), patient-reported outcomes (PROMIS scores), patient's activation measure, and HERTH hope index we will implement a CACE approach to control for the bias produced by not-fully adherent patients.

Just as with the case of our primary outcome, we will use a patient's randomization assignment as an instrument for HCP PLUS Peer Support group adherence. For this analysis we will define as

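### For repeated secondary outcomes, the SAP plans to estimate 3-, 6- and 9-month differences only after a significant overall interaction, which leaves null outcomes without intervals and selects larger estimates

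*Combined protocol and SAP*

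**What the plan says.** The SAP's Statistical Analysis section sets out the rule for secondary outcomes in three steps.

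- The model: "Differences in change in outcome from baseline to 3, 6, and 9-months between the study groups will be assessed by including interaction terms" between time and study group.
- The first test: "We will assess significance by first testing the overall interaction between time and group".
- The condition: "If the overall interaction is significant for an outcome measure, we will then estimate and test individual time differences accounting for multiple testing", by a Bonferroni correction.

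The Bonferroni divisor is not stated; three follow-up times suggest 3. The only significance level in that section is 0.05. It closes the survival paragraph and is not tied to the interaction test.

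The primary outcome is handled separately. The 6-month SGRQ change "will be evaluated by a hypothesis test of the interaction term between study group and the 6-month time variable", with no prior overall test and no correction.

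Under Heterogeneity of Treatment Effect, by contrast, the SAP promises subgroup estimates with 95% confidence intervals and attaches no significance condition.

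**The concern.** Controlling which results may be called significant is reasonable. Controlling which results are estimated is a different matter, and the SAP sentence ties both to the same test. Two consequences follow if it is applied literally.

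First, an outcome with a non-significant overall interaction has no planned time-specific difference or interval. A reader could not tell an outcome that excludes a useful effect from one that is merely imprecise.

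Second, time-specific estimates that appear only after a significant overall test are a selected sample. Conditional on passing, their expected size exceeds the true effect, most of all where power is low. A later meta-analysis drawing on them would inherit that bias.

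The rule reaches most of the listed secondary and intermediate outcomes, including visit counts, SGRQ domains, PROMIS scores, Herth Hope, PAM and the Understanding COPD components. None has a stated power. The SAP (Data Collection for Phase 2) also accepts that late enrollees will have no 9-month data, which lowers precision at that time.

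**Working it through.** **Evaluable number.** The SAP reports 290 enrolled, randomized 1:1, so 145 per arm. The protocol (section 7c) allows 15% attrition: 145 × 0.85 = 123 per arm.

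**The plan's own figure.** The protocol gives power 0.80, alpha 0.05, a 4-point difference and correlation 0.8, but no SD, so 145 cannot be reproduced directly. Solving n = 2(1.960 + 0.842)² × SD_change² / 4² with n = 123 gives SD_change = √(123 × 16 / 15.70) = 11.2. The cross-sectional SD is then 11.2 / √(2 × 0.2) = 17.7. This is plausible but not verifiable. Only the 123 is used below.

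**Precision.** Take SD 1 at each visit and a common correlation r among baseline and follow-up values. After adjustment for baseline:

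- SE of each between-arm difference = √(2(1 − r²)/123)
- correlation between two time-specific estimates = r/(1 + r)

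At r = 0.8: SE = √(0.72/123) = 0.0765, correlation 0.444. At r = 0.6: SE = √(1.28/123) = 0.102, correlation 0.375. The value 0.8 is the protocol's only stated correlation, given for SGRQ; 0.6 is an assumption for less stable instruments.

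**Simulation.** I drew 1,000,000 sets of three normal estimates with equal effects at 3, 6 and 9 months. I then applied a 3-df Wald test at two-sided 0.05, followed by Bonferroni (divisor 3) or Holm (divisors 3, 2, 1).

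| r | True effect (SD) | Overall test significant | Mean 6-month estimate if significant ÷ truth | 6-month power, Bonferroni | 6-month power, Holm |
|---|---|---|---|---|---|
| 0.8 | 0.10 | 25% | 1.67 | 0.12 | 0.14 |
| 0.8 | 0.20 | 80% | 1.10 | 0.57 | 0.65 |
| 0.8 | 0.25 | 95% | 1.03 | 0.80 | 0.87 |
| 0.8 | 0.30 | 99% | 1.00 | 0.94 | 0.97 |
| 0.6 | 0.10 | 17% | 1.95 | 0.06 | 0.07 |
| 0.6 | 0.20 | 56% | 1.25 | 0.31 | 0.37 |
| 0.6 | 0.25 | 77% | 1.11 | 0.51 | 0.59 |
| 0.6 | 0.30 | 91% | 1.04 | 0.70 | 0.78 |

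A true 0.20 SD is therefore reported on average as 0.22 SD (0.20 × 1.10) to 0.25 SD (0.20 × 1.25).

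**Sensitivity.**

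- Plain change scores at r = 0.8: 1.14 times at 0.20 SD.
- No use of baseline, r = 0.6: 1.55 times at 0.20 SD and 2.35 times at 0.10 SD. This is not the planned analysis.
- Effect at one time only, with 80% unadjusted power there and correlations of 0.2, 0.5 and 0.8 between the time-specific estimates: 1.17, 1.08 and 1.00 times.
- No true effect: no directional bias, but the mean absolute estimate after a significant test is about 1.6 SE, against 0.8 SE without selection.

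**Is a correction needed after the overall test?** Yes. With one large effect and two true nulls, the overall test followed by unadjusted tests has family-wise error 0.078 to 0.097. With Bonferroni/3 it is 0.027 to 0.033. Holm after the overall test stays at or below 0.049, even with divisors 2, 2, 1, which reject at least as often as the standard ones used in the table.

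**The case against.** The strongest reply is that the sentence describes a significance procedure and not a reporting policy. It follows directly on a statement about assessing significance. The preceding sentence, on assessing differences through interaction terms, carries no condition. Protocol section 7c plans the same assessment with no overall test. The coefficients exist in the fitted model whatever the test shows. Other analyses are also unconditional: "Exploratory analyses will be performed cross-sectionally at baseline, 3, 6, and 9 months post-discharge for each of the outcomes across the two study groups", and for several secondary outcomes "we will implement a CACE approach to control for the bias produced by not-fully adherent patients".

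Part of this stands. A reader might infer that the published estimates will be exaggerated. The documents do not support that, because nothing in them says what will be withheld from publication. A reader might also infer that every secondary outcome is caught. That is wrong: Morisky adherence is listed at 6 months only, so there is no set of times to screen, and time to death or first COPD-related visit is analysed by Kaplan-Meier and log-rank outside the rule.

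The substitutes do not fill the gap, however. The cross-sectional analyses are for distributions, missingness and quality assurance and are not the adjusted intention-to-treat contrast. The complier analysis targets a different quantity. If it were reported for an outcome that failed the overall test, a complier effect could stand without its intention-to-treat counterpart. Having a coefficient in the model output does not commit anyone to report it.

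On Bonferroni, the objection succeeds. It is valid, it controls the family-wise error, and it yields matching simultaneous intervals directly, which Holm does not. Calling it an error would be wrong; Holm is only a more powerful alternative.

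**Conclusion.** The concern holds for secondary and intermediate outcomes with several follow-up times. As written, the SAP conditions estimation on significance and leaves outcomes that fail the overall test with no planned adjusted difference or interval. Estimates reported only after passing are biased away from zero by about 10% to 25% at 0.20 SD, by about 70% to 95% at 0.10 SD, and by at most 4% at 0.30 SD.

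These figures assume 123 evaluable per arm at every visit, normal continuous outcomes, equal effects over time, correlation 0.6 to 0.8, baseline adjustment and a two-sided 0.05 overall test. They do not carry over directly to visit counts or binary outcomes. Missing 9-month data would lower power at that visit and so tend to raise the inflation there. The true power of each secondary outcome is not given, so no single figure can be assigned to this trial.

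The primary conclusion and the error rates claimed for it are untouched. This is a cheap improvement in how secondary results are presented, not a flaw that threatens the trial.

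**What to change.** In the SAP's Statistical Analysis section, separate estimation from testing:

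1. Report the adjusted between-arm difference (or ratio, for count and binary outcomes) with a 95% CI at every collected time for every repeated secondary and intermediate outcome, whatever the interaction p-value. This matches what the SAP already promises for subgroups.
2. If the overall interaction test is kept, use it only to decide which time-specific results may be called significant.
3. State its significance level, the family of times, and the divisor.
4. As a refinement, replace Bonferroni with Holm within each outcome's set of times. It never rejects less than Bonferroni and keeps family-wise control. At 0.20 to 0.30 SD it adds about 5 to 8 points of 6-month power in five of the six scenarios above, and 3 points in the sixth, where power is already 0.94. Do not simply drop the correction.

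The cost is SAP wording and longer tables. Holm gives no simple matching simultaneous intervals, so the 95% CIs should be labelled as unadjusted for multiplicity. An interval may then exclude no effect while the Holm test is not significant, and the table notes should say so.
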